2.3 Analysis

The analysis was chosen before collecting baseline survey data. The syntax in Stata© is included at the end of this section. The analysis will be conducted using an analysis by intention to treat (ITT) and will include all available data, maintaining participants as members of their allocated group. The following research questions will be addressed:

Pupil level

and baseline testing process. As a result, there is a difference of 2 schools between the intervention and control groups, partly because randomisation occurred over two waves of recruitment.

⁹ This is the achieved sample size for the primary outcome (Externalising behaviours-SDQ)

- ERQ1: What is the mean difference in externalising behaviour, measured by the Strengths and Difficulties Questionnaire (SDQ) subdomains of Conduct Problems and Hyperactivity, between CYP in intervention settings receiving TISUK training and CYP in control settings receiving business as usual at follow-up?
- ERQ2: What is the mean difference in internalising behaviour, measured by the Strengths and Difficulties Questionnaire (SDQ) subdomains of Emotional Problems and Peer Problems, between CYP in intervention settings receiving TISUK training and CYP in control settings receiving business as usual at follow-up?
- ERQ3: What is the mean difference in prosocial behaviour, measured by the SDQ subdomain of Prosocial behaviour, between CYP in intervention settings receiving TISUK training and CYP in control settings receiving business-as-usual at follow-up?
- ERQ4: What is the mean difference in Total Difficulties, measured by the SDQ subdomain of Conduct Problems, Hyperactivity, Emotional Problems and Peer Problems, between CYP in intervention settings receiving TISUK training and CYP in control settings receiving business-as-usual at follow-up?
- ERQ5: What is the mean difference in non-psychotic psychological distress, measured by the General Health Questionnaire (GHQ), between CYP in intervention settings receiving TISUK training and CYP in control settings receiving business as usual at follow-up?
- ERQ6: What is the mean difference in well-being, measured by the Short Warwick Edinburgh Well-being Scale (SWEMWBS), between CYP in intervention settings receiving TISUK training and CYP in control settings receiving business as usual at follow-up?
- ERQ7: What is the mean difference in the sense of connectedness, measured by the School Connectedness Scale, between CYP in intervention settings receiving TISUK training and CYP in control settings receiving business as usual at follow-up?
- ERQ8: What is the mean difference in the percentage of exclusions between CYP in intervention settings receiving TISUK training and CYP in control settings receiving business as usual at follow-up?
- ERQ9: What is the mean difference in the percentage of suspensions between CYP in intervention settings receiving TISUK training and CYP in control settings receiving business as usual at follow-up?
- ERQ10: What is the mean difference in the percentage of attendance between CYP in intervention settings receiving TISUK training and CYP in control settings receiving business as usual at follow-up?

- ERQ11: What is the mean difference in all primary and secondary CYP outcomes between CYP in intervention settings who received TISUK training and CYP in control settings who received business as usual, considering sub-group analysis by sex, ethnicity, and free school meal (FSM) eligibility?

School staff level

- ERQ12: What is the difference in attitudes related to trauma-informed care (TIC) of school staff, measured by the Attitudes Related to Trauma-Informed Care (ARTIC) survey, between school staff in the intervention setting receiving TISUK training and school staff in control settings receiving business as usual at follow-up?
- ERQ13: What is the difference in well-being, measured by the SWEMWBS, between school staff in the intervention setting receiving TISUK training and school staff in control settings receiving business as usual at follow-up?

School level

- ERQ14: What is the difference in the percentage of school staff retention at the school level between schools in the intervention setting receiving TISUK training and schools in control settings receiving business as usual at follow-up?
- ERQ15: What is the difference in the percentage of school staff sickness at the school level between schools in the intervention setting receiving TISUK training and schools in control settings receiving business as usual at follow-up?
- ERQ16: What is the difference in the percentage of CYP suspensions at the school level between schools in the intervention setting receiving TISUK training and schools in control settings receiving business as usual at follow-up?
- ERQ17: What is the difference in the percentage of CYP exclusions at the school level between schools in the intervention setting receiving TISUK training and schools in control settings receiving business as usual at follow-up?
- ERQ18: What is the difference in the percentage of CYP school attendance in the targeted years at the school level between schools in the intervention setting receiving TISUK training and schools in control settings receiving business as usual at follow-up?
- ERQ19: What is the difference in the percentage of CYP school suspensions/exclusions/attendance in the targeted years at the school level between schools in the intervention setting receiving TISUK training and schools in control settings

receiving business as usual at follow-up, considering sub-group analysis by sex, ethnicity, and free school meal (FSM) eligibility?

As evidence suggests, the distribution of the externalising behaviour subscale of the SDQ is normally distributed (Caldwell et al., 2021); thus, the primary analysis will take the form of a multilevel model with random effects at school considering pupils are nested within schools and this may introduce variation. The model will include the binary treatment variable and be adjusted for baseline stratification covariates¹⁰ and the baseline value of the outcome.

We are employing a random-effects approach to model the cluster-level effects at the school level in our trial. This approach allows us to treat schools as random samples from a broader population, enabling the generalizability of our findings beyond just the sampled schools. Moreover, the random-effects model incorporates partial pooling or shrinkage, which can lead to better predictions of school-level effects compared to a fixed-effects approach. Crucially, with a sufficient number of school clusters (more than 10 or 20) in our sample, we can reliably estimate the between-cluster variance and make valid inferences about the variability of school-level effects, providing insights into the impact of school-level factors on the outcome of interest (Rabe-Hesketh & Skrondal, 2008).

Secondary outcomes will be assessed similarly by establishing diagnostic plots to explore the distribution and identify the most appropriate regression approach, including stratification factors and baseline covariates within a multilevel model. These plots include residual plots to check for violations like non-linearity and heteroscedasticity, normal probability plots to assess the normality of residuals, and histograms of residuals to identify potential outliers.

Outcomes at the individual level (CYP and school staff) will be analysed using multilevel modelling, while outcomes at the school level will be done through linear regression. Table 5 sets out the statistical analysis for each outcome by level.

Table 5 Statistical analysis by outcome and level

Outcome	Level	Model	Covariates
Primary outcome Externalising behaviour	CYP	Multilevel model	Pre-treatment scores of outcomes at CYP level

¹⁰ This refers to the binary variable indicating whether the school is above or below the median proportion of FSM6 students

Secondary outcomes Internalising behaviour Non-psychotic psychological distress Well-being Sense of connectedness Exclusions, suspensions and attendance at individual (CYP) level			Demographic factors (sex, FSM status) at CYP level
Secondary outcomes Attitudes related to TIC Well-being	School Staff	Multilevel model	Pre-treatment scores of outcomes at staff level
Secondary outcomes Staff retention Staff sickness Exclusions & suspensions of CYP School attendance of CYP	School	Linear regression (OLS)	Pre-treatment scores of outcomes at the school level

The syntax in Stata© would be as below, using the ‘mixed’ command:

```
Full adjusted model: mixed post-treatment_outcome TISUK baseline_outcome fsm || school_id
```

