	70	0.1272	0.1284	0.1298	0.1317	0.1341
	60	0.1374	0.1385	0.1402	0.1422	0.1449

Rationale for Targeting 100 Schools

Targeting 100 schools and 16,000 students is justified by several considerations. First, a larger pool of schools increases the likelihood of recruiting a diverse population of school types (e.g., school-level of deprivation, FSM, different socioeconomic backgrounds) and student demographics, enabling robust subgroup analyses and generalizability of findings across various contexts. Second, a large overall sample size enhances statistical power to detect smaller but potentially meaningful intervention effects, minimising the risk of false negatives and providing reliable findings to inform future interventions. Third, the target sample size was selected to ensure sufficient power for the quasi-experimental design (QED) analysis focused on a targeted subgroup of students. Lastly, a larger sample size accommodates the cluster randomised trial design, accounting for potential clustering effects and maintaining adequate power for the primary analysis.

Table 4 displays the minimum detectable effect in the protocol according to the assumed parameters, target sample size, and the respective effect size after randomisation driven by the achieved number of responses on the primary outcome. Thus, while the MDES in the protocol is an estimation from the assumptions, the MDES estimated in the column 'Randomisation' corresponds to the actual achieved sample size at baseline in the primary outcome from the schools that were randomised. As we are adopting an intention-to-treat approach, the estimation includes responses from 4 schools that dropped out after randomisation.⁵ Those four schools that dropped out belong to the intervention group.

⁵ This means that now the number of schools in the trial are 74 with 4 dropping out from the intervention group after randomisation

Table 4 Sample size calculations and effects size

		Protocol	Randomisation
Minimum Detectable Effect Size (MDES)		0.1064	0.094
Pre-test/ post-test correlations	level 1 (participant)	n/a	n/a
	level 2 (cluster)	n/a	n/a
Intracluster correlations (ICCs)	level 1 (participant)	n/a	n/a
	level 2 (cluster)	0.03	0.015
Alpha		0.05	0.05
Power		0.8	0.8
One-sided or two-sided?		Two-sided	Two-sided
Average cluster size		160⁶	166⁷
Number of clusters	intervention	50	40
	control	50	38
	Total	100	78 ⁸

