⁶ Average school size in England is 986, average year size is 200 and accounting for a potential 20% not consenting, hence, cluster size 160.

⁷ This is the actual cluster average size

⁸ Although the initial plan was to allocate schools equally to the intervention and control groups at the randomisation stage, the achieved sample showed a slight difference due to attrition during the recruitment

		Protocol	Randomisation
Number of participants	intervention	8,000	6,391
	control	8,000	7,214
	Total	16,000	13,393 ⁹

The MDES calculations were performed using PowerUp! Tool, developed by Dong and Maynard (2013), which incorporates the formula below according to Bloom, Richburg-Hayes, and Black (2007), for the two-level cluster randomised controlled trials:

$$MDES = M_{n-k*-2} \sqrt{\left(\frac{\rho(1 - R_C^2)}{P(1 - P)J}\right) + \left(\frac{(1 - \rho)(1 - R_i^2)}{P(1 - P)Jm}\right)}$$

Employing this formula enables the inclusion of baseline covariates at the cluster (school) level, pupil level, or both. Our analysis strategy intends to use mean-centered baseline scores within the multilevel models at both the pupil and school levels. Incorporating a covariate at both levels - school and pupil - enhances the trial's precision, resulting in a reduced Minimum Detectable Effect Size (MDES) estimate compared to methodologies that employ only one covariate or none.

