2.3.1 Primary outcome analysis

The primary outcome combines the Conduct Problems and Hyperactivity sub-scales of the Strengths and Difficulties Questionnaire (SDQ) to measure externalising behaviours.

We will employ a two-level multilevel model to account for the clustered nature of our data, where students are nested within schools. This modelling approach assumes that the schools included in the study represent a random sample from the broader population of schools. Multilevel models are well-suited for analysing hierarchical data structures and appropriately handling the variability within schools (among students) and between schools in terms of

outcomes. These models can effectively capture and model the complex sources of variation at multiple levels of the hierarchy (Bosker & Snijders, 2011).

The two-level **random-intercept model** is described by:

$$Y_{ij} = \beta_1 + TISUK_j\tau + (Baseline_{ij})\beta_2 + FSM_j\beta_3 + \mu_j + \varepsilon_{ij}$$

- Y_{ij} is the outcome for pupil i in school j ;
- $TISUK_j$ is a binary variable denoting whether a school is assigned to the intervention (1) or the control (0);
- $Baseline_{ij}$ represents pupil-level pre-test covariates and demographic characteristics at baseline for pupil i in school j .
- FSM_j is a binary indicator denoting whether a school is above the median proportion of FSM6 (1) or below (0).
- μ_j are the school level residuals [$\mu_j \sim i. i. d N(0, \sigma_\mu^2)$]
- ε_{ij} are the individual level residuals [$\varepsilon_{ij} \sim i. i. d N(0, \sigma_\varepsilon^2)$]

This is a random intercept model because $\beta_{1j} = \beta_1 + \mu_j$ corresponds to the school-level intercept for school j and $\beta_{1j} \sim i. i. d N(\beta_1, \sigma_\mu^2)$. The total variance is decomposed into two portions: the between-school variance (μ_j) and the within-school variance (ε_{ij}). The target parameter of the intervention is the average effect on pupil outcomes captured by τ .

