2.3.10 Intra-cluster correlations (ICCs)

In this trial, the units forming clusters are schools. The Intraclass Correlation Coefficients (ICCs) will be computed for the baseline measure of the primary outcome, externalising behaviour, using an empty multilevel model without covariates. The ICC will be estimated at the school level, as this is the clustering level in the study design.

Specifically, a two-level random intercept model will be fitted, with children and young people (CYP) at level 1 nested within schools at level 2. The ICC will be calculated using the following formula:

$$ICC = \frac{\sigma_{School}^2}{(\sigma_{School}^2 + \sigma_{CYP}^2)}$$

Where σ_{School}^2 is the variance at the school level, and σ_{CYP}^2 is the variance at the CYP level.

The 'estat icc' command within Stata© 17 will be used to obtain the ICC estimate and its corresponding confidence interval from the empty multilevel model¹³.

¹³ This has already been estimated on baseline data

Additionally, the ICC will be estimated from the primary analysis model, which includes covariates and other predictors, to assess the impact of adjusting for these variables on the clustering effect.

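### The SAP fixes neither the estimator nor the degrees of freedom for the primary multilevel model; run on software defaults, its 95% interval is about 3.5–3.7% too narrow and its 5% test runs at about 5.8–5.9%

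*SAP*

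**What the plan says.** SAP section 2.3 introduces the primary analysis as a two-level random-intercept model and prints its syntax: "mixed post-treatment_outcome TISUK baseline_outcome fsm || school_id". Section 2.3.10 names the software when it describes the intracluster correlation: the `estat icc` "command within Stata© 17 will be used to obtain the ICC estimate".

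In the model equation of section 2.3.1, treatment and the FSM indicator both carry only a school subscript, so both are school-level covariates. Section 2.3.2 applies the same equation to the remaining pupil outcomes and to the staff outcomes.

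On the number of schools, section 2.2 says of the randomisation column in Table 4 that "the estimation includes responses from 4 schools that dropped out after randomisation", which is the 78 schools randomised (40 intervention, 38 control). A footnote adds: "This means that now the number of schools in the trial are 74 with 4 dropping out from the intervention group after randomisation".

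The only remark on whether there are enough schools is in section 2.3, which says that "with a sufficient number of school clusters (more than 10 or 20) in our sample" the between-school variance can be estimated reliably. REML, Satterthwaite, Kenward-Roger and a t reference are mentioned nowhere for this model. By contrast, the SAP does specify robust standard errors for the school-level regressions (2.3.2) and clustered standard errors for the two-stage least squares analysis (2.3.9).

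**The concern.** Arm is allocated by school, so the information on its effect comes from the spread between schools, not from the 13,000 or so pupils. Two small-sample corrections follow. The between-school variance should allow for the school-level coefficients already fitted, which REML does and maximum likelihood does not. The test of arm should then be referred to a t distribution on roughly the number of schools minus those coefficients, not to the normal. The printed line asks for neither. When the between-school variance is clearly above zero, both omissions shorten the interval for the primary effect.

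The remark about 10 or 20 clusters concerns estimation of the variance component. It does not settle the reference distribution for the arm effect. Leaving the choice open also means that it could be made after outcome data are seen.

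**Working it through.** **Inputs.** Schools J = 78 or 74 (SAP 2.2). School-level coefficients q = 3: intercept, arm, FSM stratum (SAP 2.3.1). Average cluster size 166, of which a footnote to Table 4 says "This is the actual cluster average size". ICC 0.015 at baseline, 0.03 in the protocol. Two-sided alpha 0.05 (Table 4). Assumption from outside the documents: `mixed` without options fits maximum likelihood and reports z tests and intervals.

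**The plan's own figures.** The documents state no true type I error, only the nominal 0.05. The related figure is the minimum detectable effect size (MDES), from the formula in SAP 2.2 with no covariate gain: M × √[ρ/(P(1−P)J) + (1−ρ)/(P(1−P)Jm)].
- Protocol column (J = 100, m = 160, ρ = 0.03, P = 0.5): √(0.0012 + 0.0002425) = 0.03798. With a normal M of 2.80 this gives 0.1064, as stated; t on 98 df gives 0.1075.
- Randomisation column (J = 78, m = 166, ρ = 0.015, P = 40/78): 0.0930 with t on 75 or 76 df and 0.0918 with a normal M, against 0.094 stated.

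**Closed form, equal cluster sizes.** Maximum likelihood divides the between-school sum of squares by J where J − q is needed. So:
- standard-error ratio = √((J − q)/J)
- interval-width ratio = √((J − q)/J) × 1.96/t(0.975, J − q)
- true size = P(|t on J − q df| > 1.96 × √((J − q)/J))

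| | J = 78 | J = 74 |
|---|---|---|
| df = J − 3 | 75 | 71 |
| SE ratio | √(75/78) = 0.981 | √(71/74) = 0.980 |
| 1.96/t | 1.96/1.992 = 0.984 | 1.96/1.994 = 0.983 |
| Width ratio | 0.965 (3.5% too narrow) | 0.963 (3.7% too narrow) |
| Correct interval is wider by | 3.65% | 3.86% |
| Effective cut-off | 1.922 | 1.920 |
| True size | 5.84% | 5.89% |

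**Simulation.** 20,000 null trials per setting, pupil-level baseline with an assumed slope of 0.6; Monte Carlo error about 0.17 points.

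| Arms, mean cluster size, assumed size CV, ICC | ML + z | REML + z | REML + t (J − 3) |
|---|---|---|---|
| 40 v 38, 166, 0, 0.015 | 5.82% | 5.33% | 4.93% |
| 40 v 38, 166, 0.35, 0.015 | 5.80% | 5.36% | 4.98% |
| 36 v 38, 166, 0.35, 0.015 | 6.07% | 5.49% | 5.09% |
| 36 v 38, 115, 0.35, 0.015 | 5.99% | 5.44% | 5.10% |
| 36 v 38, 166, 0.35, 0.03 | 5.76% | 5.29% | 4.97% |

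The mean of the ML + z column is 5.9%, and the simulated width ratio is 0.962 to 0.965. REML with z still runs at 5.3–5.5%, so both parts of the correction are needed.

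**Sensitivity.**
- *Fewer schools.* At 60 schools, the lowest row of the SAP's retention tables, the interval is 4.6% too narrow and the size is 6.1%.
- *School-mean baseline.* SAP 2.2 says baseline scores will enter at both levels, although the printed line has only one baseline term. Adding the school-level term makes q = 4: size 6.0% at 78 schools and 6.1% at 74; interval 4.2% and 4.4% too narrow.
- *ICC near zero.* The variance component is then often estimated as zero. With equal clusters, 78 schools and 2 million draws, ML + z runs at about 4.6% at ICC 0 (30 or 130 per school) and REML + t at about 4.1%. At ICC 0.005 with 30 per school, ML + z runs at about 5.4%.

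**The case against.** The strongest reply is that the printed line is shorthand, not a commitment to maximum likelihood. It uses a placeholder outcome name, it omits the pupil sex and FSM status that Table 5 lists as covariates, and neither document states the estimator. This stands in part. The exact statement is that estimator and reference distribution are unspecified, and that the size given here follows if the line is run as printed. It does not remove the point, because nothing else in the plan would lead an analyst to anything but the default.

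The second reply is that the effect is trivial. Coverage falls from 95% to about 94.2%, and the stated MDES of 0.094 is less than half the funder's ceiling of 0.20, so no design decision turns on it. That stands, and it sets the severity.

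A reader might infer two stronger claims that the documents do not support:
- *That the error always favours finding an effect, on every pupil and staff outcome.* It does not when the ICC is near zero. The documents give no staff ICC or staff cluster size, so for staff outcomes neither size nor direction is known.
- *That planning used t and analysis uses z.* The MDES formula does carry a degrees-of-freedom subscript, but the protocol's 0.1064 reproduces only with a normal multiplier, and 0.094 matches neither version exactly.

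**Conclusion.** The gap is real and small. If the line is run as printed on Stata defaults, the 95% interval for the primary effect is about 3.5–3.7% too narrow and the nominal 5% test runs at about 5.8–5.9%, with 78 or 74 schools and an ICC of 0.015 or 0.03. The excess is under one percentage point and would change a conclusion only for a borderline p-value.

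The result rests on the software default, on three school-level coefficients, and on an ICC at follow-up that is clearly above zero. The simulation also assumes a pre-post slope of 0.6 and cluster-size CVs of 0 and 0.35, neither of which is in the documents; the closed form needs neither and agrees closely. Low severity, but worth settling before outcome data are analysed.

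**What to change.** Add `reml dfmethod(kroger)` (or `reml dfmethod(satterthwaite)`) to the line in SAP 2.3. State in 2.3.1 and 2.3.2 that confidence intervals and p-values for arm in the unweighted pupil and staff mixed models use those degrees of freedom.

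Section 2.3.8 plans multiple imputation when between 5% and 40% of outcomes are missing, so state there that pooled inference on arm uses a matching t reference on school-level degrees of freedom. The weighted multilevel models of the embedded quasi-experimental study are outside this change.

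The cost is one change to the code, a few sentences, and intervals about 4% wider (3.65% at 78 schools, 3.86% at 74). In the simulations above this brings the size back to 4.9–5.1%. For an outcome with an ICC near zero the corrected test is somewhat conservative (about 4.1% at ICC 0).
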